	
 4) Females who tested positive for urine pregnancy test; 5) Subjects with acute febrile disorders, infectious disease, or a history of SARS; 6) Axillary temperature > 37.0 °C; 7) Subjects with serious cardiovascular diseases, such as arrhythmia, heart block, myocardial infarction, and serious, uncontrolled hypertension despite antihypertensive drugs (on-site measurement: SBP ≥ 180 mmHg and DBP ≥ 110 mmHg); 8) Subjects with serious chronic diseases or progressive diseases that cannot be controlled, such as diabetes or thyroid disorders; 9) Subjects with congenital or acquired angioedema/neurogenic edema; 10) Subjects with a history of urticaria within 1 year prior to receiving the investigational vaccine; 11) Subjects with asplenia or functional asplenia; 12) Subjects with lung function abnormalities such as chronic obstructive pulmonary disease or pulmonary fibrosis; 13) Subjects with a history of COVID-19 infection/disease; 14) Subjects with epidemiological exposure to SARS-CoV-2, or travel history to areas of moderate/high risk or abroad within the past 21 days; 15) Those who are judged by the investigator with any contradiction to the study protocol or the signing of informed consent being affected due to various medical, psychological, social, or other conditions.
Duration	Approximately 6 months
Principal Investigator (PI)	
Name: [name] Title: Chief Physician Position: Deputy Director of Jiangsu Provincial Center for Disease Control and Prevention Institution: Jiangsu Provincial Center for Disease Control and Prevention (Public Health Research Institute of Jiangsu Province) Address: [name] Postcode: 210009 [contact] [contact] E-mail: [contact]

Co-PI	
Name: [name] Title: Chief Physician Position: Director, Department of Vaccine Clinical Evaluation, Jiangsu Provincial Center for Disease Control and Prevention Institution: Jiangsu Provincial Center for Disease Control and Prevention Address: [name] Postcode: 210009 [contact] E-mail: [contact]

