7.3 Exclusion Criteria

- 1) Subjects with a history or family history of convulsions, epilepsy, encephalopathy, or mental disorders;
- 2) Subjects who are allergic to any ingredient of the investigational vaccine, or subjects with a history of severe anaphylactic reactions to vaccines, allergies, or asthma;
- 3) Those with a history of severe vaccine-related ARs following immunization with a vaccine;
- 4) Females who tested positive for urine pregnancy test;
- 5) Subjects with acute febrile disorders, infectious disease, or a history of SARS;
- 6) Axillary temperature > 37.0 °C;
- 7) Subjects with serious cardiovascular diseases, such as arrhythmia, heart block, myocardial infarction, and serious, uncontrolled hypertension despite antihypertensive drugs (on-site measurement: SBP ≥ 180 mmHg and DBP ≥ 110 mmHg);
- 8) Subjects with serious chronic diseases or progressive diseases that cannot be controlled, such as diabetes or thyroid disorders;
- 9) Subjects with congenital or acquired angioedema/neurogenic edema;
- 10) Subjects with a history of urticaria within 1 year prior to receiving the investigational vaccine;

- 11) Subjects with asplenia or functional asplenia;
- 12) Subjects with lung function abnormalities such as chronic obstructive pulmonary disease or pulmonary fibrosis;
- 13) Subjects with a history of COVID-19 infection/disease;
- 14) Subjects with epidemiological exposure to SARS-CoV-2, or travel history to areas of moderate/high risk or abroad within the past 21 days;
- 15) Those who are judged by the investigator with any contradiction to the study protocol or the signing of informed consent being affected due to various medical, psychological, social, or other conditions.

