8 METHODS AND PROCEDURES

8.1 Selection of Subjects

The recruitment for the clinical trial will be performed at the study site approximately two weeks prior to visit 1 (V1). The number of subjects to be enrolled is about 1.5 times of the sample size (may be adjusted according to the actual situation). Investigators with relevant experience will perform such recruitment.

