8.7.2 Contents and parameters of safety observation

Based on the types and incidence of ARs observed in previous clinical trials as well as the ARs listed in the package inserts of similar products available on the market, this study has adhered to the "Guidelines for Grading Criteria of Adverse Reactions in Clinical Trials of Preventive Vaccines" (No. [2019]102 issued by NMPA). The contents and parameter grades of post-vaccination safety observations are presented in Tables 8.7-1 to 8.7-3, and the grading of vital sign-related safety is shown Table 8.7-4.

Table 8.7-1. Grading of administration-site (local) AEs of the nebulized inhalation vaccine

Symptoms/Signs	Grade 1	Grade 2	Grade 3	Grade 4
Dry mouth	Transient, not requiring treatment, and not affecting daily activities	Dry mouth, slightly affecting daily activities	Seriously affecting daily activities and requiring treatment	NA
Hoarseness	Transient, not requiring treatment, and not affecting daily activities	Hoarseness, affecting normal speech	Seriously affecting daily activities and requiring treatment	NA
Mucositis oral	Transient, not requiring treatment, and not affecting daily activities	Slightly affecting daily activities	Seriously affecting daily activities and requiring treatment	NA
Throat swelling	Transient, not requiring treatment, and not affecting daily activities	Throat redness and swelling, slightly affecting swallowing function	Seriously affecting daily activities and requiring treatment	NA
Pharyngalgia	Transient, not requiring treatment, and not affecting daily activities	Pain pharynx, slightly affecting daily activities	Severe pharyngalgia, seriously affecting daily activities, and requiring drug treatment	NA

Table 8.7-2. Grading of injection-site (local) AEs of the intramuscular vaccine

Symptoms/Signs	Grade 1	Grade 2	Grade 3	Grade 4
Pain	Not affecting or slightly affecting limb activities	Affecting limb activities	Affecting daily activities	Leading to loss of basic self-care ability or hospitalization
Induration*, swelling** #	Diameter of 2.5 cm to < 5 cm or area of 6.25 cm ² to < 25 cm ² and not or slightly affecting daily life	Diameter of 5 cm to < 10 cm or area of 25 cm ² to < 100 cm ² or affecting daily life	Diameter ≥ 10 cm, or area ≥ 100 cm ² , or ulceration, secondary infection, phlebitis, aseptic abscess, or wound drainage, or seriously affecting daily activities	Abscess, exfoliative dermatitis, or necrosis of dermal or deep tissues

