8.7.6 Reporting procedures for serious adverse events

In case of any SAE, whether or not related to the investigational vaccines, the investigator must complete the "Serious Adverse Event Reporting Form" after being informed and report it to the PI and the vaccine manufacturer via fax or email within 24 h. The report should include a description, onset, type, duration, causality with vaccination, outcome, and treatment (symptomatic treatment) of the AE.

Upon receipt of a SAE report, the study center should confer with the investigator to determine if the subject should continue or discontinue trial participation in consideration of the duration, range, intensity, and outcome of the AE, as well as the subject's will. The study center should determine if the SAE is a SUSAR; if so, the study center should report it to the Center for Drug Evaluation, NMPA and the PI, and the PI should report the SUSAR to the Institutional Review Board.

For SUSARs which are fatal or life-threatening, the study center should, after the first knowledge, report them to the Center for Drug Evaluation, NMPA as soon as possible (not more than 7 natural days), report within the following 8 days and complete the follow-up information.

For SUSARs which are not fatal or life-threatening or other potentially serious safety risk information, the study center should, after the first knowledge, report to the Center for Drug Evaluation, NMPA (not more than 15 natural days). The investigator should record SAEs truthfully and evaluate and discuss them in the final report after trial completion or termination.

Table 8.7-4. Contact information of the Institutional Review Board

Institutional Review Board of Jiangsu Provincial Center for Disease Control and Prevention	Contact: [name] [contact]	E-mail: [contact]
--	--------------------------------------	---------------------

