8.9 On-Site Workflow

8.9.1 Overview of visit procedures

From the beginning of the screening prior to the enrollment to the end of the study, the subjects will complete all the study content in 5 or 6 visits. The specific time, time window, and content for each visit are detailed in 8.9-1.

Table 8.9-1. Visit procedures

Visit point	V1	V2	V3	V4	V5
Visit time	D-7-D0	D14	D28	Month 3	Month 6
Time window	/	± 3 days	± 5 days	± 15 days	± 15 days
Informed consent	•				
Registration/identity verification	•	•	•	•	•
Physical examination (blood pressure, height, weight, body temperature)	•				
Urine pregnancy (female of childbearing potential)	•				
Medical history inquiry and eligibility screening	•				
Randomization number assignment ^a	•				
Immunogenicity blood sampling ^a	10 mL	10 mL	10 mL	10 mL	10 mL
Cellular immunity blood sampling ^b	15 mL	15 mL			
Saliva sampling ^c	2 mL	2 mL	2 mL	2 mL	2 mL
Immunization ^d	•				
Dispensation of diary card (0–14 days)	•				
Return of diary card (0–14 days)		•			
Dispensation of diary card (after 14 days)					
Return of diary card (after 14 days)			•		
Safety observations ^e	•	•	•		
SAE observation and reporting ^f	•	•	•	•	•

- Immunogenicity group only;
- Subjects in the immunogenicity group recruited from Jiangsu CDC who are included in cellular immunity group only;
- Immunogenicity group only;
- If the investigator believes the health status of the subject on the day of vaccination is temporarily unsuitable for vaccination, the dose may be delayed up to 1 week;
- All adverse events within 0–28 days after immunization should be observed and documented, regardless of whether related to the vaccine;
- The investigator should fill out the "Serious Adverse Event Report Form" and complete the initial report within 24 h of learning of an SAE and complete the final report at the end of the event. Except for subjects in the immunogenicity subgroup, all subjects should complete V4–V5 via telephone

Table 8.9-2. Sample collection schedule at clinical trial visits

Visit	V1	V2	V3	V4	V5
Visit time	D0	D14	D28	Month 3	Month 6
Immunogenicity [#]	10 mL	10 mL	10 mL	10 mL	10 mL
Saliva [#]	2 mL	2 mL	2 mL	2 mL	2 mL
Cellular immunity [@]	15 mL	15 mL			

Note: # Immunogenicity group only

@ Subjects in the Jiangsu CDC who are included in cellular immunity group only

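### Exclusion 7 joins its two blood pressure cut-offs with 'and' and ties them to treated hypertension, so some severe readings miss the only measured limit

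*Protocol*

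**What the plan says.** Exclusion 7 rules out serious cardiovascular disease and gives several examples. The last is "serious, uncontrolled hypertension despite antihypertensive drugs (on-site measurement: SBP ≥ 180 mmHg and DBP ≥ 110 mmHg". The synopsis carries the same bracket, "on-site measurement: SBP ≥ 180 mmHg and DBP ≥ 110 mmHg", so this is not a difference between synopsis and body.

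Blood pressure is taken from every subject at V1. Table 8.9-1 lists "Physical examination (blood pressure, height, weight, body temperature", and section 8.4 requires the same examination. Neither gives a cut-off. Section 8.4 has an interviewing physician screen each subject against the inclusion and exclusion criteria, and only those who pass may be enrolled.

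Three other provisions could stop or postpone a subject with high blood pressure:

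- item 8 of section 7.3, on serious chronic or progressive disease that cannot be controlled;
- item 15, which leaves exclusion to the investigator on medical or other grounds;
- the immunization note to Table 8.9-1, under which, if the investigator finds a subject "temporarily unsuitable for vaccination, the dose may be delayed up to 1 week".

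None of the three states a blood pressure value.

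**The concern.** A numeric limit in an eligibility list exists so that an extreme reading stops vaccination without anyone having to weigh it. The sponsor chose 180 and 110 mmHg as the marks of serious, uncontrolled hypertension. As worded, the bracket works only when both are reached together, and only for hypertension that persists on drugs. Isolated severe systolic or diastolic readings fall outside it, and so does severe hypertension that nobody has yet treated.

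What is at stake is subject safety and consistency between sites. The protocol plans about 10,420 adults in six centers, with at least 30% aged 60 or over, and section 6.3.2 allows several vaccination sites per center. If the stop depends on judgement, the same reading may be excluded at one site and vaccinated at another.

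**Working it through.** The protocol gives no figure to reproduce. The check is one of logic, followed by a search for any other limit.

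**1. The rule as written.** The numeric test in item 7 is met when all three of these hold: the subject has hypertension despite antihypertensive drugs; SBP ≥ 180 mmHg; DBP ≥ 110 mmHg.

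**2. Example readings.** The readings below are illustrations, not data from the trial. 'Met' refers to the bracketed test alone, not to exclusion 7 as a whole.

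| Reading (mmHg) | On drugs | SBP ≥ 180 | DBP ≥ 110 | As written | Only 'and' changed to 'or' | 'Or', with or without drugs |
|---|---|---|---|---|---|---|
| 185/112 | yes | yes | yes | met | met | met |
| 210/100 | yes | yes | no | not met | met | met |
| 170/115 | yes | no | yes | not met | met | met |
| 210/120 | no | yes | yes | not met | not met | met |

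The second and third rows show the gap caused by 'and'. The fourth row shows a separate gap caused by the treatment condition, which a one-word change does not close.

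**3. Is there another measured limit?**

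- Section 8.4 and Table 8.9-1 require the measurement and set no value.
- Tables 8.7-1 to 8.7-3 grade no blood pressure reading. Section 8.7.2 says that "the grading of vital sign-related safety is shown Table 8.7-4", but the table with that number is headed "Table 8.7-4. Contact information of the Institutional Review Board". The reference concerns grading after vaccination and would not have set an entry limit in any case. It is mentioned only because it is the one other place where a blood pressure value might be sought.
- Item 6, "Axillary temperature > 37.0 °C", is the other vital sign with an entry limit. It involves no treatment condition and no second measurement.

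Exclusion 7 is therefore the only numeric blood pressure stop before vaccination.

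**4. What remains for a reading that misses the test.** The wider wording of item 7 (its list of examples is open), items 8 and 15, and the dose-delay note. All can be applied to a subject at 210/100, and all require someone to decide.

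**The case against.** The best case for the current text has four parts.

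*The bracket need not be read jointly.* The same sentence uses 'and' to list alternative diseases, and nobody would require all of them. The bracket could likewise be listing one systolic and one diastolic limit, and the word may be a slip of translation. This is possible, but for two thresholds on one measurement the joint reading is the more natural one. If sites could read it either way, that is a reason to clarify it. The treatment condition is open to a similar defence, namely that the on-site reading was meant to count by itself, and has the same remedy.

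*The criterion is wider than the bracket.* This stands. A reader might infer that the protocol admits subjects at 210/100 or 170/115. The documents do not support that. A physician screens every subject, item 7 excludes serious cardiovascular disease in general terms, and item 15 and the delay note add further stops. Several other exclusions, such as items 9 and 11, also have no measured limit. What can be said is only that these subjects miss the numeric test.

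*No harm is shown.* This also stands. Nothing in the protocol says that an isolated elevation raises the risk from a single inhaled or injected dose. Emergency equipment is required on site (section 8.6), and all subjects are observed for 30 minutes (section 8.7.1). How strict to make an entry cut-off is the sponsor's choice. But the sponsor has already chosen the cut-offs, and the point asks only that each should work when it is exceeded.

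*The contrast with temperature proves little.* Agreed. Item 6 has a single measurement, so the question of joining two limits could not arise there. The point does not depend on it.

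**Conclusion.** The point holds as a minor subject-safety correction. On the literal reading, a treated subject over just one cut-off, or an untreated subject over both, does not meet the protocol's only measured blood pressure limit and is kept out by investigator judgement alone. This assumes that 'and' is read jointly and that the treatment condition is taken at its word.

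Its size cannot be put in numbers. The protocol gives neither the share of volunteers with such readings nor the share of those whom investigators would turn away, and no defensible range can be drawn from it.

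A reader might also infer that the safety or immunogenicity results are compromised. They are not: sample size, power, alpha and the comparison of arms do not depend on this wording.

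**What to change.** In the synopsis and in section 7.3, reword the hypertension part of item 7 as: *serious, uncontrolled hypertension (on-site measurement: SBP ≥ 180 mmHg or DBP ≥ 110 mmHg, with or without antihypertensive drugs)*. Keep both cut-offs. Both changes are needed: 'or' closes the gap for treated subjects over one limit, and moving the treatment condition closes it for untreated subjects.

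No new procedure is required, because blood pressure is already measured at V1. The cost is some extra screen failures, whose number cannot be estimated from the documents. Section 8.1 plans for a margin: "The number of subjects to be enrolled is about 1.5 times of the sample size". Taken at face value that is 1.5 × 10,420 = 15,630 volunteers, a surplus of 15,630 − 10,420 = 5,210. The factor is approximate and adjustable, and the surplus must also absorb every other screen failure, whose rate is not stated. It therefore shows that there is a margin, not that the margin is enough.

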7.4 Premature Termination Criteria

Premature termination refers to the situation where the subject fails to attend the end visit specified in the protocol, no further study procedures are required, no further follow-up is required, and no more information of the subject is collected since the last visit.

- 1) Subjects request to withdraw from the clinical trial;
- 2) Failing to complete the study process by leaving the observation area is deemed as voluntary withdrawal;
- 3) The subject's health status causes inappropriateness for study participation;
- 4) Any other reasons deemed by the investigator.

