Subjects assigned to receive an ICV booster dose will receive the vaccine from the same manufacturer as the two-dose prime immunization. All subjects will be issued diary cards on the day of vaccination and on Day 14 after vaccination for systematic safety observations. Venous blood and saliva samples will be collected from subjects in the immunogenicity group on the day of vaccination as well as 14 days, 28 days, 3 months, and 6 months after vaccination to test for serum antibody titers, serum IgA, and SIgA. Venous blood samples will be collected from subjects in the cellular immunity group on the day of vaccination and 14 days after vaccination to test for cellular immunity. All subjects are required to complete interviews on the day of vaccination as well as 14 and 28 days after vaccination. Subjects in the immunogenicity group are also required to complete 3- and 6-month follow-up visits. The remaining subjects may complete the 3- and 6-month visits via telephone follow-up. When about 2000 subjects (first stage) and 5000 subjects (second stage) are enrolled, the safety of all subjects in the early stage should be evaluated, and the enrollment schedule should be continued with the consent of PI. Enrollment will be suspended

or terminated immediately if a safety issue with vaccination is found to meet the suspension or termination criteria.

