8.7 Safety Follow-Up and Evaluation

8.7.1 Safety observation

All subjects will remain on site for a 30-min observation period after receiving the vaccination. Investigators will observe each and every one of the subjects and record both regional and systemic responses reported during the 30-min observation period, as well as their severity.

A safety follow-up will be performed within 14 days after vaccination for all subjects, during which the investigator will systematically examine each subject for ARs, and the subject will fill in the "Vaccination Diary Card (Within 14 Days)" according to their symptoms and signs. From day 15 to day 28 after vaccination, post-vaccination AEs should be observed through spontaneous reporting and regular follow-ups. The investigators will inquire and check the diary cards at the next visit and guide the subjects in completing the cards. From day 28 to month 6 after vaccination, safety follow-ups on SAEs should be performed by spontaneous reporting.

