8.7.5 Handling of adverse reactions/events

AE: an unexpected medical event a subject experiences during the clinical trial, which is not necessarily caused by or related to the vaccine/vaccination.

AR: an unexpected or untoward reaction during the vaccination at the prescribed dose and according to prescribed procedures, which is usually related to vaccination.

Serious adverse event (SAE): an important medical event not necessarily caused by or related to clinical trials of vaccines, which leads to: 1) death; 2) life-threatening situation; 3) hospitalization or prolonged hospitalization; 4) permanent or significant disability/incapacity; 5) congenital anomaly or birth defect; or 6) other important medical events that may cause the conditions above without treatment.

Suspected unexpected serious adverse reaction (SUSAR): A suspected AR refers to an untoward and unintended reaction at any dose, analyzed to be at least possibly related to the drug; an unexpected AR refers to that the nature, severity, outcome, or frequency of the AR is inconsistent with the expected risks described in the protocol or other relevant information (e.g., the Investigator's Brochure and package insert).

Subjects should report any clinically significant diseases/events after vaccination to the investigator in a timely manner. The investigator should follow up the AR/AE until the symptoms disappear or become stable. Necessary treatment and management will be provided unconditionally when deemed necessary by the investigator in order to relieve the subject from suffering from the AR/AE. All medications and medical management will be recorded during each follow-up.

If a SAE/SAR occurs, the investigator should take necessary measures immediately, complete the "Serious Adverse Event Report Form", and report it to the PI and the study center via fax or email within 24 h.

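### Section 7.4 stops data collection for vaccinated subjects terminated for reasons other than withdrawal of consent, so later adverse reactions and SAEs can be missed

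*Protocol*

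**What the plan says.** Protocol section 7.4 defines premature termination as missing the end visit, with the consequence that study procedures cease and "no further follow-up is required, and no more information of the subject is collected since the last visit". Four grounds follow:

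1. the subject asks to withdraw;
2. the subject leaves the observation area with the study process unfinished, which counts as withdrawing voluntarily;
3. a ground of health, in the words "health status causes inappropriateness for study participation";
4. whatever reason the investigator sees fit.

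The same consequence attaches to all four.

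Other sections bear on this:

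- Section 8.6.2: one dose, given at V1.
- Section 6.1: the primary safety endpoint is adverse reactions over days 0–28. SAEs over 6 months are a secondary safety endpoint.
- Section 8.7.5: "The investigator should follow up the AR/AE until the symptoms disappear or become stable".
- Section 8.7.6: after an SAE, the study center and the investigator decide whether the subject continues in the trial, looking at features of the event and the subject's wishes.
- Section 8.7.1: from day 28 to month 6, "safety follow-ups on SAEs should be performed by spontaneous reporting".
- Section 6: "The remaining subjects may complete the 3- and 6-month visits via telephone follow-up". The visit table (Table 8.9-1) marks SAE observation at V4 and V5, and its note f has everyone outside the immunogenicity subgroup complete those visits by telephone.

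**The concern.** In a trial with repeated dosing, a health-related withdrawal stops further exposure. Here nothing is left to stop after V1, so terminating a vaccinated subject only closes the record. Section 7.4 does not distinguish a subject who refuses further contact, where collection must end, from one whom the site terminates for health or other reasons and who could still be contacted.

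The loss need not be random. Health status is itself a ground, and section 8.7.6 allows an SAE to lead to discontinuation. Subjects whose observation ends early may therefore be those in poorer health. What is at stake is the primary adverse-reaction incidence to day 28 and the SAE incidence to month 6. Analysis cannot recover events that were never recorded, so the rule has to be settled in the protocol.

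**Working it through.** **Passages side by side**

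| Question | One place | Another place |
|---|---|---|
| Is an adverse event still followed after termination? | 7.4: no follow-up required, no information collected, no exception stated | 8.7.5: followed until resolved or stable. Table 8.9-1 note f: an SAE needs a final report when the event ends |
| How are SAEs found from day 28 to month 6? | 8.7.1: spontaneous reporting | Table 8.9-1: SAE observation at V4 and V5, by telephone outside the immunogenicity subgroup |

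Both pairs need reconciling.

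**Which subjects can bias the result**

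Sections 8.11.4.2.3 and 8.11.4.2.4 report the number and percentage of subjects with an event. Section 8.11.3 keeps immunized subjects in the safety set and makes no exception for early termination. I take that set as the denominator. For each endpoint there are two cases:

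- The subject already had an event that counts for that endpoint before termination. The subject is in the numerator, and the percentage does not change.
- The subject had no such event before termination but has one later within the window. The subject is in the denominator only, and the percentage is too low.

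The cases are judged separately for each endpoint. A subject terminated after a non-serious reaction counts for the adverse-reaction endpoint, but a later SAE would be missed. Section 8.7.5 protects events already known, not new ones.

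**The margin in the plan's own detection figure**

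Inputs from section 6.2: n = 10,000, incidence p = 0.02% = 0.0002, probability of seeing at least one case stated as at least 85%.

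- Formula: P(at least one) = 1 − (1 − p)^n
- Plan's figure: 1 − 0.9998^10,000 = 0.865. It reproduces. The expected number of cases is 10,000 × 0.0002 = 2.
- Smallest n for 85%: ln(0.15) / ln(0.9998) = 9,484.7, so 9,485 subjects.
- Margin: 10,000 − 9,485 = 515 subjects, or 5.2%.
- If the 210 randomized recipients of the inhaled vaccine (420 / 2) are pooled in: n = 10,210 gives 0.870, and the margin is 10,210 − 9,485 = 725 subjects, or 7.1%.

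Section 6.2 adds an allowance for dropout in the immunogenicity group but states none for the safety group. The margin treats a lost subject as contributing nothing. That overstates the effect of a termination that comes late in the window or after the event.

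**The case against.** Section 7.4 can be read as a definition of who is classed as terminated, not as an instruction. It says follow-up is not required; it does not forbid it. That stands as a possible reading. But the text sits under a heading of criteria, includes grounds decided by the investigator and makes no exception for 8.7.5, so a site could follow it literally.

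The protocol also covers part of the gap. Known events are followed under 8.7.5, SAEs get a final report, and SAE observation at V4 and V5 is already in the visit table. The issue in 8.7.1 is therefore one of aligning wording, not of a missing contact. The health ground may also apply to people not yet vaccinated: the visit table allows vaccination to be delayed for health, and section 6.3.2 replaces dropouts before vaccination. The concern is limited to vaccinated subjects.

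Three stronger readings are tempting and not supported:

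- **That subjects who move away are cut off.** The text speaks only of leaving the observation area. The only place-bound observation described is the 30-minute stay after vaccination (section 8.7.1).
- **That withdrawal because of a reaction or SAE removes that event from the incidence.** That subject is already in the numerator for that endpoint.
- **That detection falls by a definite amount.** Assuming that 10% or 50% of events go unseen gives 83.5% or 63.2%, but nothing in the protocol supports either share. Section 3.4.1 says most reactions in the earlier phase II inhalation trial came within days 0–7 of a dose. That argues against large losses of common reactions, though it says less about rare ones.

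**Conclusion.** The point holds as a defect of wording with a possible downward bias. Section 7.4 applies one no-more-information rule to withdrawal of consent and to terminations in which the subject has not refused contact. That conflicts with 8.7.5. New adverse reactions to day 28, or SAEs to month 6, can be missed in vaccinated subjects terminated before an event that counts for the endpoint concerned.

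The direction of bias rests on two assumptions: that 7.4 is applied as written, and that the safety set is the denominator. The size is unknown, because the protocol gives no withdrawal rate for the safety group. The detection claim of at least 85% is correct at 86.5% but tolerates a loss of only about 5% of 10,000 subjects. That shows a thin margin, not that it will be used up. The change should be made; the finding does not undermine the design as a whole.

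**What to change.** - **Section 7.4:** for vaccinated subjects, end data collection only on withdrawal of consent to follow-up, death or confirmed loss to follow-up. Keep everyone else under AE and SAE contact through day 28 and SAE contact through month 6, by telephone if they no longer attend. Record the reason for termination separately from the end of data collection.
- **Sections 7.4 and 8.7.5:** reconcile the two, so that it is clear how events are followed after termination.
- **Section 8.7.1:** reconcile spontaneous reporting with Table 8.9-1, so that every subject is actively asked about SAEs at V4 and V5. Settle whether telephone completion is optional (section 6) or expected (note f).

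This concerns data collection only and leaves the decision in section 8.7.6 as it is. The cost is a wording amendment and a few extra calls. The V4 and V5 contacts are already scheduled. Calls up to day 28, and calls to immunogenicity-group subjects who no longer attend, would be additional.
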